19. APPENDIX H: PROTOCOL SUMMARY OF CHANGES

Any administrative changes to the protocol including spelling corrections, minor clarifications, renumbering, and reformatting are not summarized in the following table. Such changes are evident and may be reviewed in the red-lined Protocol Amendment.

Section	Change to Protocol	Rationale
Title Page, Signature Page	Date and version # changed	The date and version # changed due to this revision
Synopsis Eligibility Criteria and Protocol Section 4.3	Extended Planned study dates Added “approximately” to the Number of Investigative Sites Revised inclusion criterion #10 to add “regardless of subject’s age” for screening Pap testing requirements	To allow for a longer enrollment period To allow flexibility in the number of investigative sites To provide clarity
Protocol Sections 3 and 6.7.3.1	Added that the first screening phase cycle analysis may be repeated if the considered less than normal by the subject. The first cycle collection is discarded.	To allow for the variability in bleeding amounts women may experience
Protocol Section 4.2	Revised inclusion criterion #10 to add “regardless of age” for screening Pap testing requirements	To provide clarity
Protocol Section 5.3	Added instruction to contact the sponsor for IUS storage temperature excursions	To ensure quality of the investigational product
Protocol Sections 6	Indicated the flow chart of study assessments has been split into two; one for screening and one for enrollment and follow-up	To provide clarity
Protocol Sections 6.3, 6.7.2.3	Added that screening bloodwork does not require fasting	To provide clarity
Protocol Sections 6.7.1 and 6.7.3.7	Added details about determining if the cycle collection is likely to be less than study requirements before sending feminine hygiene products for analysis	To identify screen failures prior to feminine hygiene product analysis
Protocol Section 7.1.2	Revised to Liletta being approved for contraception for up to 6 years and more current contraceptive efficacy data	FDA approval received 15 October 2019

Protocol Sections 7.1.3.2, 7.1.3.6	Revised ectopic pregnancy rate and pelvic infection occurrence to reflect 6 years of use data	To reflect the current product package insert
Protocol Section 7.10	Revised to indicate collection of AEs to start with study treatment	To be consistent with other sections
Protocol Section 11	Added references	To be current and complete
Appendix A	Schedule of Events now split into Appendix A for screening Added additional assessments	To provide clarity To be more comprehensive

ATC	Anatomical Therapeutic Chemical
BOCF	Baseline observation carried forward
BMI	body mass index
BP	blood pressure
cm	centimeter(s)
CM	Concomitant medication
CRF	case report form
CSR	clinical study report
DDE	drug dictionary enhanced
g	gram(s)
HMB	Heavy menstrual bleeding
in	inch(es)
ITT	Intent-to-Treat
IUS	intrauterine system
kg	kilogram(s)
lb	pound(s)
l	Liter
LNG	Levonorgestrel
LOCF	Last observation carried forward
LTFU	Lost-to-follow-up
MedDRA	Medical Dictionary for Regulatory Activities
Mg	milligram(s)
mL	Milliliter
MBL	Menstrual blood loss
MITT	Modified Intent-to-Treat
N	Number
Ng	nanogram
PP	Per-Protocol
SAE	serious adverse event

SAP	statistical analysis plan
SAS	SAS® Software
TEAE	treatment-emergent adverse event
WHO	World Health Organization

DEFINITIONS

Adverse Event (AE)	An adverse event is any untoward medical occurrence in a patient or clinical investigation subject administered a pharmaceutical product and which does not necessarily have to have a causal relationship with this treatment. An AE can, therefore, be any unfavorable and unintended sign (that could include a clinically significant abnormal laboratory finding), symptom, or disease temporally associated with the use of a medicinal product, whether or not considered related to the medicinal product.
Amenorrheic (Treatment Cycle 3 and Cycle 6)	No spotting or bleeding with no feminine hygiene product use, or only spotting or light bleeding but no feminine hygiene product use, during the entire 28-day collection interval in either Treatment Phase Cycle 3 or Cycle 6.
Intent-to-Treat (ITT)	All subjects with qualifying baseline data at study entry for whom the IUS is successfully inserted.
Modified Intent-to-Treat (MITT) Population	All subjects with qualifying baseline data at study entry for whom the IUS is successfully inserted and for whom there is at least one assessment of MBL during the Treatment Phase Cycle 3 or Cycle 6. All MBL values reported for both validated and unvalidated used feminine hygiene products will be included.
Supportive MITT	A supportive subset of the MITT population with baseline and post-baseline MBL data reported collected from only validated feminine hygiene products. This population is to demonstrate the robustness of the efficacy analyses.
Per-Protocol (PP) Population	A subset of the MITT population that excludes subjects with major protocol deviations that are determined to have impact on the data of MBL assessment.

Safety Population	All subjects enrolled who had an IUS insertion attempt regardless of outcome.
Serious Adverse Event (SAE)	An adverse event that results in any of the following outcomes: death; life-threatening situation (subject is at immediate risk of death); inpatient hospitalization or prolongation of existing hospitalization; persistent or significant disability/incapacity; congenital anomaly/birth defect in the offspring of a subject who received study drug; important medical events that may not result in death, be immediately life-threatening, or require hospitalization, may be considered an SAE when, based upon appropriate medical judgment, they may jeopardize the subject and may require medical or surgical intervention to prevent one of the outcomes listed in this definition.
Treatment-Emergent AE (TEAE)	New AEs that occur and existing medical conditions that worsen during the study, beginning from the IUS insertion attempt and ending when the insertion attempt is declared a failure or on the subject's last known IUS date of use or the Safety Contact whichever is later.

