7.4 Pregnancy Assessment and Reporting

High sensitivity urine pregnancy tests are performed at each study visit. For any positive pregnancy test on IUS treatment through Visit 8/Early Discontinuation:

- Immediately obtain a serum quantitative hCG
- Within 3 calendar days conduct a transvaginal ultrasound for pregnancy confirmation, pregnancy location and date of conception
 - If the pregnancy is too early for ultrasound verification have the subject return in approximately 1-2 weeks for an unscheduled visit and repeat ultrasound examination
- Complete a Pregnancy Narrative (See Study Reference Manual)

If the subject reports a positive pregnancy test on her own (performed at home) she should be seen as soon as possible for a high-sensitivity urine pregnancy test to be performed at the clinic and if the test is positive perform the required procedures above.

For pregnancies occurring before IUS discontinuation, ultrasonography will also be used to verify presence of the IUS in the uterus.

All confirmed pregnancies occurring during study treatment will be followed to completion.

Pregnancy outcomes, including normal births, septic abortions, ectopic pregnancies, birth defects, and premature deliveries, whenever this information is available, will be obtained. Pregnancy reporting should include a Pregnancy Report Form Case Report Form (CRF) and Pregnancy Outcome CRF.

Pregnancy management is outlined in Appendix F.

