9.1 Sample Size

Eligible subjects 18-50 years of age will include approximately 100 subjects using LNG20 IUS. The sample size estimate is based on results from previous studies with similar endpoints as well as the goal of a lower 95% confidence around the point estimate of the primary outcome with acceptable precision, i.e., being no more than 10% lower than the point estimate. The estimation of the required number of subjects needed to evaluate the efficacy of the LNG20 IUS is based on the following assumptions:

- The expected successful treatment rate is estimated to be 80% or higher
- The lower bound of 95% confidence interval should be within 10% from the point estimate, i.e., 70% or higher to establish the efficacy of LNG20 IUS for the treatment of HMB
- Early discontinuations due to dropouts, IUS expulsions, pregnancies and other reasons will not exceed 15%

A sample size of 85 will provide at least 71.5% lower bound of the 95% confidence interval for an expected successful treatment rate of 80% or higher based on normal approximation.

Therefore, 100 subjects using LNG20 IUS will provide sufficient number of subjects, for the goal of approximately 85 subjects completing the trial.

Subjects who discontinue treatment for any reason other than a one-time study IUS replacement within two weeks of a complete or partial expulsion will not be replaced.

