5.3.3 Missing Data for MBL

- A MBL assessment by AH may not be collected for Treatment Phase Cycle 3 and Cycle 6 in which a subject reported being amenorrheic (no spotting/bleeding) for the 28-day collection interval on the CRF for AH Menstrual Blood Loss Assessment; in this case the corresponding MBL value will be set to 0 mL. Additionally, the participant may report spotting only or light bleeding on her diaries with no feminine hygiene products used; in this case the corresponding MBL value will be set to 0 mL
- For a Treatment Phase missed Visit 7 (Cycle 3) or missed Visit 8 (Cycle 6), no imputation of MBL from diary data alone will be conducted.
- For the evaluations of MBL, the last observation carried forward (LOCF) method will be used for imputation. If MBL data in Cycle 3 are available but no MBL data in Cycle 6 are available or Cycle 6 is invalid, then MBL data in Cycle 3 will be used as End of Study MBL.
- Additional imputation method(s) might be explored for sensitivity analysis when deemed necessary

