9.1 Menstrual Blood Loss

This study will utilize the AH method to assess MBL. During the Screening Phase all feminine hygiene products used during a menses with any evident bleeding will be analyzed. Baseline MBL will be the average of the Screening cycles evaluated. Two of three cycles must have ≥ 80 mL MBL to qualify for enrollment (Treatment Phase); if the first two cycles qualify a third cycle will not be evaluated. During the Treatment Phase, all feminine hygiene products use only during Cycle 3 (Days 57-84) and Cycle 6 (Days 141-168) will be collected for analysis and used to determine efficacy. All values of MBL reported by the lab for the above cycles for both validated and unvalidated feminine hygiene products will be included in the analysis, unless analyzed beyond the 56 days of validated stability.

MBL assessment measured from all collected feminine hygiene products will be included in the primary analysis and only study-specific validated feminine hygiene products in the supportive analyses.

The study-specific feminine hygiene products are:

- Tampax Regular Tampons with flushable applicator
- Tampax Super or Super Plus tampons with flushable applicator
- Kotex Regular Maxi Pads;
- Kotex Super Long Maxi Pads;
- Kotex Overnight Maxi Pads with Wings.
- Carefree Body Shape Pantiliners with Actifresh, Extra Long

A MBL assessment by AH may not be collected for Treatment Phase Cycle 3 and Cycle 6 in which a subject reported being amenorrheic (no spotting or bleeding) on the CRF for AH Menstrual Blood Loss Assessment; in this case the corresponding MBL value will be set to 0 mL. In the case that no feminine hygiene products were used by the participant due to spotting only the MBL value will be set to 0 mL.

Any feminine hygiene product collection would be considered “invalid” for the following:

- Analyzed beyond the 56 days of validated stability (from start of feminine hygiene collection).
- Any feminine hygiene product collection for a Treatment Phase cycle for which it was discovered during the post-collection interval study visit (i.e., Visit 7 for Cycle 3 and Visit 8 for Cycle 6) that the study IUS was not present
- Technical issue at the lab in analyzing the product leading to unreportable results

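### The SAP scores a bleed-free Cycle 3 or 6 as 0 mL without asking about pregnancy, so a pregnancy first found at Visit 7 or 8 can count as a treatment success

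*SAP*

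**What the plan says.** The Definitions section of the SAP classes a treatment cycle as amenorrheic when the woman reports "No spotting or bleeding with no feminine hygiene product use, or only spotting or light bleeding but no feminine hygiene product use" over the whole 28-day interval. The definition gives no MBL value. Two later sections do that. SAP 5.3.3 says of such a cycle that "in this case the corresponding MBL value will be set to 0 mL". SAP 9.1 repeats the rule for a cycle "in which a subject reported being amenorrheic (no spotting or bleeding) on the CRF for AH Menstrual Blood Loss Assessment".

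SAP 9.1 lists three grounds on which a collection is invalid: analysis beyond 56 days, a laboratory failure, and absence of the IUS. The last is worded "Any feminine hygiene product collection for a Treatment Phase cycle for which it was discovered during the post-collection interval study visit" (Visit 7 or Visit 8) "that the study IUS was not present". Pregnancy is not a ground. It is also not among the major deviations in SAP 7.2.

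Under SAP 5.3.3, "If MBL data in Cycle 3 are available but no MBL data in Cycle 6 are available or Cycle 6 is invalid", the Cycle 3 value becomes the end-of-study value. Under SAP 6 and 9.2, baseline is carried forward in the ITT analyses only when both cycles lack a result.

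Elsewhere pregnancy is treated as an end to treatment. Protocol 7.17.1 lists it among the reasons for withdrawal from treatment, and the sample-size assumptions in Protocol 9.1 count it as attrition: "Early discontinuations due to dropouts, IUS expulsions, pregnancies and other reasons will not exceed 15" percent. Protocol 7.4 states that "High sensitivity urine pregnancy tests are performed at each study visit".

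**The concern.** A missed period caused by pregnancy is not an effect of the IUS on heavy bleeding. The 0 mL rule cannot tell the two apart, and 0 mL always meets both success criteria (below 80 mL, and no more than half of baseline). An event that the protocol treats as ending treatment can thus be recorded as the best possible primary outcome.

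The plan also treats the same event in two ways. A pregnancy that leaves no Cycle 3 or Cycle 6 result is a failure in the ITT analysis through baseline carried forward. A pregnancy that suppresses bleeding through a complete interval is a success there. The misclassification can only raise the success rate, and the ITT analyses meant to test the MITT result would not reveal it.

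**Working it through.** **1. Can the case arise under the schedule?** Visit 7 falls on Days 85 to 105, Cycle 6 is Days 141 to 168, and Visit 8 falls on Days 169 to 189 (Protocol 6.9.3 and 6.10, Appendix B). Between the two visits the only scheduled event is a reminder contact on Days 133 to 140, for which Appendix B lists no pregnancy test. The gap between scheduled tests is therefore 64 days (169 − 105) to 104 days (189 − 85). A pregnancy begun in that gap can first be found at Visit 8, after a bleed-free Cycle 6. For Cycle 3 (Days 57 to 84) the preceding test is at Visit 6, Days 28 to 42, so the gap is shorter.

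**2. How is she scored?**

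| Analysis | Found at Visit 8, both cycles present | Found at Visit 7, then withdrawn |
|---|---|---|
| MITT | Cycle 6 = 0 mL: success | Cycle 3 = 0 mL carried forward: success |
| Both ITT analyses | Success (baseline carried forward needs both cycles missing) | Success, for the same reason |
| PP | Stays in; success | Can be excluded: missing the Cycle 6 analysis is a listed major deviation |
| Supportive MITT | Not stated for a cycle with no products | Not stated |

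**3. What is it worth?** The SAP uses the normal approximation, lower limit = p − 1.96·√(p(1 − p)/n), with a criterion of at least 70%. The plan's own figures reproduce at p = 80%:

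- n = 80: 0.80 − 1.96·√(0.16/80) = 71.2% (SAP 4)
- n = 85: 0.80 − 1.96·√(0.16/85) = 71.5% (Protocol 9.1)

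The same formula with affected women rescored:

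| Starting point | One recoded as failure | Two recoded as failures | One removed |
|---|---|---|---|
| 64/80: 71.2% | 63/80: 69.8%, not met | – | 63/79: 70.9%, met |
| 68/85: 71.5% | 67/85: 70.1%, met | 66/85: 68.8%, not met | 67/84: 71.2%, met |
| 80/100: 72.2% | 79/100: 71.0%, met | 78/100: 69.9%, not met | – |

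**4. How many women?** The documents do not say, because the pregnancy-rate text in Protocol 7.1.2 is redacted. If 0 to 1% conceive in six months (an assumption), that is 0 to 1 of about 100. Only those undetected and bleed-free through a full interval count, so the expected number is lower still.

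**5. The absent-IUS gap without pregnancy.** After an unnoticed expulsion with normal cycles resumed, the chance that a fixed 28-day interval holds no bleeding is (L − b − 28 + 1)/L, for cycle length L and b bleeding days, and zero when this is negative. Protocol 4.2 admits cycles of 21 to 35 days; b is assumed. At L = 35 and b = 5 the result is 3/35 = 8.6%; with b = 7 it is 1/35 = 2.9%; with b = 5 and L of 32 days or less it is zero.

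**The case against.** Several points on the other side stand.

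- **The event is rare and there are safeguards.** Women are told to call for an urgent visit if they suspect pregnancy (Protocol 6.8.2), a positive home test leads to a clinic test (7.4), and early discontinuation outside a complete window yields no collection (6.10). These narrow the route but do not close it.
- **One woman seldom decides the trial.** At the planned 80% rate, recoding one success still passes at n = 85 and n = 100. The binomial chance of landing exactly on the smallest passing count (64/80, 67/85 or 79/100) is about 10% at a true rate of 80%, and about 3 to 5% at the 85% that Protocol 7.1.1 cites for a similar product. That chance must be combined with the small chance that an affected pregnancy occurs.
- **Scoring pregnancy as failure is a choice.** Removal from the analysis is another, and in the tightest case above the two give different answers. That supports fixing the rule in advance, not leaving it open.

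A reader might infer that every planned analysis is affected. The documents do not support that: PP can exclude a woman withdrawn at Visit 7, and the Supportive MITT, restricted to validated products, does not say how it handles a cycle with no products.

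A reader might also infer that a bleed-free woman whose IUS was expelled certainly keeps her 0 mL. SAP 9.1 already shows the intent to void such a cycle, and SAP 5.3.3 speaks of Cycle 6 itself being invalid. The fair reading is that coverage of an assigned zero is unstated, not that it is ruled out.

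**Conclusion.** The point holds for pregnancy. SAP 5.3.3 and 9.1 assign 0 mL to a bleed-free, no-product Cycle 3 or Cycle 6 with no pregnancy condition, and nothing else in the SAP removes the value. The result is a success in the MITT and both ITT analyses, and in PP when both cycles are present.

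For an absent IUS the finding is narrower: a gap in the wording of a rule whose purpose is clear.

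The expected effect is small, 0 to 1 woman of about 100 on an assumed conception rate, but it runs only in the product's favour. It would change the conclusion only near the boundary, as at 64 of 80. The correction is worth making because it is cheap and because, once such a case is known, the choice between failure and removal would be made with the result in view.

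**What to change.** 1. In SAP 5.3.3 and 9.1, state that 0 mL is neither assigned nor kept for an interval that overlaps a confirmed pregnancy, and add this as a fourth invalid ground. Overlap can be judged from the conception date that Protocol 7.4 already has the ultrasound establish.
2. State that the pregnancy and absent-IUS grounds apply to assigned 0 mL values as well as to collected products. Rely on what is found at Visits 7 and 8; a single check cannot show that the IUS was in place throughout the interval, so do not require that.
3. State how a woman with a voided value is then scored. Voiding alone does not settle it. Under the present rules a void Cycle 6 falls back to her Cycle 3 value, while a void Cycle 3 with no Cycle 6 takes her out of the MITT and makes her a failure by baseline carried forward in the ITT. One clear option is to count her as unsuccessful in at least the ITT sensitivity analysis.

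The cost is a few sentences in the SAP. The pregnancy tests and IUS checks at Visits 7 and 8 are already planned, so no procedure changes. The success count may fall by about one woman.

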6.11 Safety Follow-Up

All subjects for whom the IUS was removed will be contacted 7 to 10 days after the study exit visit to assess for any post-IUS removal bleeding and cramping (if applicable), and any IUS-related or IUS procedure-related adverse events. After completion of the Treatment Phase, all subjects with ongoing IUS-related adverse events that are not resolved or stabilized will have monthly contacts or visits, as appropriate, until the event is resolved or stabilized.

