7.6 Definition of an Adverse Event

An **adverse event** is any untoward medical occurrence in a patient or clinical investigation subject administered a pharmaceutical product and which does not necessarily have to have a causal relationship with this treatment. An AE can therefore be any unfavorable and unintended sign (that could include a clinically significant abnormal laboratory finding), symptom, or disease temporally associated with the use of a medicinal product, whether or not considered related to the medicinal product. The Investigator should attempt to establish a diagnosis of the event based on signs, symptoms, and/or other clinical information. In such cases, the diagnosis should be documented as the AE/SAE and not the individual signs/symptoms.

- Any medical condition or clinically significant laboratory abnormality with an onset before the study IUS insertion is considered to be pre-existing and should not be documented in the CRF as an AE, but should be recorded as medical history.
- Any AE (i.e., a new event or an exacerbation of a pre-existing condition) with an onset from the beginning of study IUS insertion through Visit 8/Early Discontinuation and the post-Treatment Phase safety contact (if applicable) should be recorded.
- All AEs must be recorded regardless of the severity or relationship to study medication.
- All AEs that result in permanent discontinuation of the investigational product must be reported, whether serious or non-serious.
- An AE **does** include:
 - exacerbation of a pre-existing illness
 - increase in frequency or intensity of a pre-existing episodic event or condition
 - condition occurring after study IUS insertion
 - continuous persistent disease or symptoms present at baseline that worsen following the start of the study
- An AE **does not** include:
 - medical or surgical procedures (e.g., surgery, endoscopy, tooth extraction, transfusion); the condition that leads to the procedure may be an adverse event if the condition has worsened since enrolling in the study

- pre-existing diseases or conditions present or detected prior to start of study drug administration that do not worsen
- situations where an untoward medical occurrence has not occurred (e.g., hospitalization for elective surgery, social and/or convenience admissions)
- disease or disorder being studied or sign or symptom associated with that disease
- overdose of concomitant medication without any signs or symptoms

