- If, during on-study contact with the subject she reports that the IUS is no longer in place, the date of reported expulsion/removal if known, or if unknown the date of contact minus 1 day, will be used as the last date associated with IUS use.
- In the cases of subjects who are lost to follow-up or withdraw consent prior to Visit 8 and a last contact date is available, the last contact date- date of insertion ($i_{usindt}+1)/28$ will be used. If not contact date after insertion is available then date of IUS insertion + 1 day will be used as the last date associated with IUS use.

Similarly, for subjects who had a successful IUS insertion but who have not yet had any post-insertion data (e.g., Visit 6, Visit 7, Visit 8, unscheduled visit) retrieved at the site which could be used to directly calculate duration of use, the IUS insertion date +1 day will be used as the last date of IUS use for the purpose of analysis. For the summary of duration of product use, all subjects with ≥ 1 days of product use, as defined in this section, will be included in the calculations.

5.5 28-Day Cycles of Use Calculation

In addition to the calculation of 28-day cycles based on last date of IUS use as described in [Section 5.4](#), each recorded diary date between the IUS insertion date and the last calculated date of product use, inclusively, is compared to the IUS insertion date in order to calculate cycle number and day. Duration of use expressed as the number of 28-day cycles is then calculated as the maximum duration (ceiling value) between the IUS insertion date and last recorded diary date.

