11.1 Adverse Events

Menstrual bleeding and cramping/pain are recorded in a daily subject diary and not on the Adverse Events CRF. The subject daily diary has been designed to collect IUS and menstrual bleeding and cramping AEs following insertion of the study IUS. Menstrual bleeding or cramping/pain would only be entered onto the general AE CRF if:

- Bleeding or cramping/pain meet serious criteria; an SAE report would also have to be submitted (this exception is due to data system requirements)
- Bleeding or cramping/pain result in the IUS being removed (this exception is due to data system requirements)

- Bleeding or cramping/pain is not related to the IUS or a menstrual condition

All adverse event summaries will be restricted to treatment-emergent adverse events (TEAE), defined as AEs occurring during or after attempted IUS insertion and those pre-attempted IUS insertion existing medical conditions that worsened during the study up to the subject's last known IUS date of use or, for subjects who have discontinued, through the safety contact after the subject's last known IUS date of use. If an AE cannot be determined as treatment-emergent, it will be counted as such.

Verbatim terms on case report forms will be mapped to preferred terms and system organ classes using the Medical Dictionary for Regulatory Activities (MedDRA) dictionary. Each adverse event summary will be displayed by treatment group. Summaries that are displayed by system organ class and preferred terms will be ordered by descending order of incidence of system organ class and preferred term within each system organ class. Summaries of the following types will be presented:

- Overall subject summary of AEs, SAEs, and deaths
- Subject incidence of TEAEs and total number of unique TEAEs by MedDRA system organ class and preferred term.
- Subject incidence of TEAEs by MedDRA system organ class, preferred term, and highest severity. At each level of subject summarization a subject is classified according to the highest severity if the subject reported one or more events. AEs with missing severity will be considered severe for this summary

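### The SAP's two TEAE definitions conflict for failed insertions, and both stop before the Early Discontinuation visit after a complete, unreplaced expulsion

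*SAP*

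**What the plan says.** The SAP defines a treatment-emergent adverse event (TEAE) twice.

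- **SAP Definitions:** the period is given as "beginning from the IUS insertion attempt and ending when the insertion attempt is declared a failure", and the sentence goes on: "or on the subject's last known IUS date of use or the Safety Contact whichever is later".
- **SAP Section 11.1:** "All adverse event summaries will be restricted to treatment-emergent adverse events (TEAE), defined as AEs occurring during or after attempted IUS insertion", together with pre-existing conditions that worsen. The period runs to last known IUS use or, "for subjects who have discontinued, through the safety contact after the subject's last known IUS date of use". It names no endpoint for a failed insertion. An event that cannot be classified is counted as treatment-emergent.

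SAP Section 5.4 sets the last date of use, for a woman who reports that the IUS is no longer in place, as "the date of reported expulsion/removal if known, or if unknown the date of contact minus 1 day".

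The protocol's recording period is wider. Under Section 7.6, events with onset from the start of insertion "through Visit 8/Early Discontinuation and the post-Treatment Phase safety contact (if applicable) should be recorded". Section 7.16 requires reporting for all enrolled women from IUS discontinuation through the Safety Follow-up. Section 6.11 says who receives that contact: "All subjects for whom the IUS was removed will be contacted 7 to 10 days after the study exit visit". The footnote to the follow-up contact in Appendix B has the same limit.

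**The concern.** The AE tables are TEAE-only, so the end of the TEAE period decides which recorded events are tabulated. SAP Section 1 gives the SAP precedence over the protocol where they differ on analysis, so the protocol's wider recording period does not repair a narrower SAP window.

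The women at issue are those in whom insertion failed or the device was lost. They belong to the Safety Population whatever the outcome of insertion, and Section 11.1 keeps all of that population in the denominator of the incidence rates. If their later events leave the numerator, the error can only lower incidence. Expulsion, bleeding, perforation and infection are also the events that Protocol Section 7.3 singles out for monitoring.

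The two definitions also differ from each other, so two programmers working from the same SAP could produce different AE tables.

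**Working it through.** The plan states no figure for this point, so there is none to reproduce. The check applies both definitions to illustrative onset days and then estimates scale.

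**Rules applied.** Definitions: the window ends at the latest of failure declaration, last use and Safety Contact, using whichever of these exist. Section 11.1: it ends at last use or, for a discontinued woman, at the safety contact. If neither exists, the default of counting the event can apply.

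**Cases** (days chosen for illustration):

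1. Insertion fails on Day 1, no contact, new event on Day 4. The Definitions window ends on Day 1, so the event is outside. Section 11.1 yields no end date, so the event can be read as counted. The definitions conflict.
2. First attempt fails on Day 1, second succeeds on Day 20, event on Day 10. Inside both.
3. Complete expulsion on Day 40, not replaced, discontinuation visit on Day 50, no safety contact, event on Day 45. Both windows end on Day 40, so the event is outside both, yet within the protocol's recording period. The default for unclassifiable events does not help, because both dates are known.
4. As case 3, but a safety contact takes place on Day 58. Inside both.
5. Partial expulsion on Day 40, IUS removed on Day 42, safety contact on Day 50, event on Day 45. Inside both.
6. Removal on Day 169, safety contact on Day 177, event on Day 172. Inside both.

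Only cases 1 and 3 fail.

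**Scale.** Inputs: first-year expulsion rate 3.9% in women with heavy menstrual bleeding (Protocol Section 7.1.5), six 28-day cycles = 168 days, and about 100 women enrolled.

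- Constant hazard: 100 × [1 − (1 − 0.039)^(168/365.25)] = 1.8 expulsions. With 85 women it is 1.5.
- All first-year expulsions falling within the first six cycles: 100 × 0.039 = 3.9.

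These count every expulsion. Partial or replaced ones are not exposed to the gap. The readable text gives no insertion-failure rate, so case 1 cannot be sized. One event in 100 women is 1 percentage point of incidence.

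**The case against.** A reader who stops at the words on failed insertion might infer that the window always closes at failure or at expulsion, and that every later event vanishes from every AE table. The documents do not support that.

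- The Definitions sentence continues to a latest-of rule, so a woman with a safety contact is followed to that contact.
- A partially expelled IUS is removed (Protocol Appendix G), which brings the safety contact with it. A replaced IUS carries its own later last-use date (SAP Section 5.4).
- After a failed insertion, Section 11.1 has no cutoff and leans towards counting. Protocol Section 6.8.2 requires no follow-up when there is no related event. Where a related event is being followed, its onset is already inside the window.
- Bleeding and cramping TEAEs come from diary check boxes (SAP Sections 11.3 and 11.4), which state no end rule. Expulsion itself has its own Kaplan-Meier analysis (Section 11.6).
- Individual data are listed in full (Section 5.1), and serious events still go to the sponsor.

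A reader might also infer a gap of many weeks. An expulsion just after a Day 42 visit with exit at Visit 7 (Day 85 to 105) gives 85 − 42 = 43 to 105 − 42 = 63 days. That is a worst case. Women are told to call for an urgent visit after an expulsion (Protocol Section 6.8.2), and an unknown expulsion date leaves a gap of only about one day. It is not impossible, since SAP Section 9.1 foresees the IUS being found absent only at Visit 7 or Visit 8.

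It can also be argued that Protocol Section 7.16, which covers all enrolled women, implies a safety contact after complete expulsion. It sets a reporting duty up to that follow-up, but Section 6.11 and Appendix B, which say who is contacted, name only removal.

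These points narrow the concern to cases 1 and 3. They do not remove it.

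**Conclusion.** The concern holds in two specific situations. After a failed insertion with no later IUS use and no Safety Contact, the two SAP definitions disagree. Loss of later events from the tables is then possible but not established. After a complete, unreplaced expulsion with a known date and no safety contact, both definitions end at expulsion, and events recorded between then and the Early Discontinuation visit are left out of the summaries while remaining in the listings.

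The number of women is likely small: of about 2 expulsions per 100 (constant hazard) or about 4 (all early), only the complete and unreplaced ones count, plus an unknown number of failed insertions. Being in one of these groups is also not the same as losing an event, because a new event must start in the gap and be reported. The sizing assumes that the cited first-year rate applies to this trial. The expulsion finding assumes that safety contacts follow the protocol's wording. The change should still be made: the rule is wrong as written, it errs in one direction, and it is easily corrected.

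**What to change.** Use one TEAE definition, worded identically in the SAP Definitions and Section 11.1. End the window at the latest of last known IUS use, Visit 8/Early Discontinuation, the Safety Contact and, after a failed insertion, the last study contact at which adverse events are recorded. This brings the tables into line with the recording period in Protocol Sections 7.6 and 7.16, and does not alter who is contacted or when.

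The cost is a wording change and one derivation on data already collected. The downside is that AE counts may rise slightly.
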